### 15. STUDY ADMINISTRATION

#### 15.1 STUDY INVESTIGATORS

Participating Investigators will be qualified based on professionals experienced in facelift surgery, such as plastic or cosmetic surgeons. Investigators will be selected based on interest and availability for participation in the study; ability to provide qualified subjects; adequate support staff; experience conducting clinical research; and willingness to comply with the protocol, IRB requirements, regulatory requirements (including the signed investigator

 APYX™ MEDICAL Apyx Medical Corporation	
Protocol Number: APX-21-04	Effective Date: March 19, 2024 Revision No: 7.0
Title: Histological Evaluation of Human Skin Biopsies to Assess the Effects of Renuvion APR Treatment as an Adjunct Procedure in Facelift Surgery	

agreement and statements disclosing any financial relationship investigators might have with Apyx Medical Corporation), and applicable regulations.

## 15.2 AMENDMENT POLICY

The investigator will not make any changes to this protocol without prior written consent from the Sponsor and subsequent approval by the IRB, except if the deviation from the protocol is necessary to protect the life and physical well-being of a subject in an emergency. Such protocol deviations must be reported to the Sponsor and the reviewing IRB as soon as possible, but no later than five working days after the emergency occurred.

Any permanent change to the protocol, whether it is an overall change or a change for specific study center(s), must be handled as a protocol amendment. Any amendment to the protocol that appears indicated as the study progresses will be fully discussed by the investigator(s) and the Sponsor. If agreement is reached regarding the need for an amendment, the Sponsor will write it. The written amendment must be submitted to the chairman of the IRB identified with this responsibility. Except for “administrative amendments”, investigators must await IRB approval of protocol amendments before implementing the change(s). Administrative amendments are defined to have no effect on the validity of the data or information resulting from the completion of the approved protocol, or the relationship of likely patient risk to benefit relied upon to approve the protocol; the scientific soundness of the investigational plan or protocol; and the right, safety or welfare of the human subjects involved in the investigation. When, in judgment of the chairman of the IRB, the investigators and/or the Sponsor, the amendment to the protocol substantially alters the study design and/or increases the potential risk to the subject, the currently approved written Informed Consent Form will require similar modification. In such cases, repeat informed consent will be obtained from subjects enrolled in the study before continued participation.

## 16. CONFLICT OF INTEREST POLICY

The independence of this study from any actual or perceived influence is critical. Therefore, any actual conflict of interest of persons who have a role in the design, conduct, analysis, publication, or any aspect of this trial will be disclosed and managed. Furthermore, persons who have a perceived conflict of interest will be required to have such conflicts managed in a way that is appropriate to their participation in the trial. The study leadership has established policies and procedures for all study group members to disclose all conflicts of interest and will establish a mechanism for the management of all reported dualities of interest.

## APPENDIX A: PATIENT SATISFACTION QUESTIONNAIRE (PSQ)

Please have the subject complete this assessment while referring to their image in the mirror and current post-treatment photos compared to baseline photos. Provide the subject with a mirror.

Using a mirror and reviewing your post-treatment photos, compare how your treatment area currently looks compared to your pre-treatment photos.

### 1. Do you notice any improvement in the appearance of your lower face?

- ☐ YES →
- ☐ Improved skin dryness/skin feels more hydrated
- ☐ Improved elasticity/pliability
- ☐ Skin quality is improved
- ☐ Skin appears more youthful
- ☐ Improved skin radiance/"glow"
- ☐ Other: \_\_\_\_\_
- ☐ NO

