### 4. STUDY DESIGN AND ENDPOINTS

#### 4.1 DESCRIPTION OF THE STUDY DESIGN

This study is a prospective, single-arm clinical study to be conducted at up to three clinical sites in the US. Up to 10 subjects will be enrolled and treated if they meet the inclusion/exclusion criteria and provide written informed consent.

Enrolled subjects meeting all entrance criteria and confirmed eligible for study treatment will be asked to participate. Subjects will receive a lower facelift surgery per the Investigator's standard clinical practice and treatment with the Renuvion APR System. The mid/upper-face area will not be treated with Renuvion and the lower face/neck area will be treated with Renuvion. Treatment will consist of subdermal coagulation of soft tissue using the Renuvion APR handpiece.

Standardized images will be taken prior to treatment and during each follow-up visit using the site's camera system. Baseline assessments and pre-treatment images should be obtained within 30 days of the study treatment.

 Apyx Medical Corporation	
Protocol Number: APX-21-04	Effective Date: March 19, 2024 Revision No: 7.0
Title: Histological Evaluation of Human Skin Biopsies to Assess the Effects of Renuvion APR Treatment as an Adjunct Procedure in Facelift Surgery	

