## 4.3 STUDY OUTCOME MEASURES

1. Change in histology evaluation of biopsy tissue between the untreated portion of the face and the Renuvion treated portion at the D180 visit and compared to baseline.
2. Analysis of all adverse events through the D180 follow-up visit.
3. Analysis of bruising post-procedure.
4. Analysis of swelling post-procedure.
5. Healing profile.
6. Analysis of bleeding during surgery.
7. The Principal Investigator will complete a PGAIS assessing overall aesthetic improvement in the treatment area at day 45, 90, and 180 post-treatment.
8. The subject will complete a SGAIS assessing overall aesthetic improvement in the treatment area at day 45, 90, and 180 post-treatment.
9. The subject will complete a Patient Satisfaction Questionnaire (PSQ) at the 180-day follow-up visit.
10. Change in estimated biological skin age from baseline to D180.

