### 2. How would you characterize your satisfaction with the treatment?

- ☐ Very Satisfied
- ☐ Satisfied
- ☐ Slightly Satisfied
- ☐ Neither Satisfied nor Dissatisfied
- ☐ Slightly Dissatisfied
- ☐ Dissatisfied
- ☐ Very Dissatisfied

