### 3. Would you recommend this treatment to your friends and family members (*check one*)?

- ☐ YES ☐ NO

*Thank you for completing this questionnaire.*

Subject Initials: \_\_\_\_\_

Date: \_\_\_\_\_ (DD/MON/YYYY)

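### PSQ item 1 cannot record worse hydration, elasticity or skin quality, so the only structured subject report on these attributes runs in one direction

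*Combined protocol and SAP*

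**What the plan says.** Section 4.3 lists Outcome 9 as follows: "The subject will complete a Patient Satisfaction Questionnaire (PSQ) at the 180-day follow-up visit". It names no item, score or success threshold, and Section 10.1 plans descriptive statistics only.

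The form is in Appendix A. Subjects work with a mirror and photographs and are told to "compare how your treatment area currently looks compared to your pre-treatment photos". Item 1 then asks "Do you notice any improvement in the appearance of your lower face". Under YES are five named boxes, among them "Improved skin dryness/skin feels more hydrated" and "Improved elasticity/pliability"; the other three cover skin quality, youthfulness and radiance. There is also a free-text other. The alternative to YES is an unqualified NO.

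Item 2 asks "How would you characterize your satisfaction with the treatment" on seven categories. Item 3 asks "Would you recommend this treatment to your friends and family members" with YES or NO.

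Section 3 gives the study purpose as Renuvion's effect on elasticity and hydration as indicators of skin quality, together with estimated biological skin age. On the design, Section 4.1 states: "Subjects will receive a lower facelift surgery per the Investigator's standard clinical practice and treatment with the Renuvion APR System".

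**The concern.** A question that offers only improvement yields only counts of improvement. A subject whose skin became drier or stiffer has no place to say so in item 1. That subject leaves a box blank or ticks NO, and looks the same as a subject with no change.

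Worsening is not far-fetched on the protocol's own terms. Section 2.2.1 lists transient migratory firmness among the expected effects, and fibrosis and subcutaneous induration among the risks.

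The gateway adds two difficulties. It asks about lower-face appearance in people who have just had a lower facelift, so a YES may reflect the surgery. It also makes a judgement of appearance the entry condition for boxes about qualities that are at least partly felt. At stake is how a tabulation of item 1 will be read: a list of improvement percentages on the study's own target attributes, with nothing beside it to show the other direction.

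**Working it through.** The plan gives no figure for the PSQ, so there is none to reproduce. The check compares the response options and then bounds what item 1 leaves unknown.

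**1. Options that can express a negative answer**
- PSQ item 1: five named improvement boxes plus other under YES, and one NO. Options for worsening: 0.
- PSQ item 2: 3 satisfied + 1 neutral + 3 dissatisfied = 7. Negative: 3 of 7.
- PSQ item 3: YES or NO. Negative: 1 of 2.
- Subject GAIS (Section 4.3.4.2, Table 2.2): 3 improved + 1 no change + 3 worse = 7. Negative: 3 of 7.

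**2. Which of these ask about hydration, elasticity or skin quality**

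Only item 1. Item 2 concerns satisfaction, item 3 recommendation, and GAIS overall aesthetic change. The instruments that can go negative do not ask about the attributes, and the one that asks about them cannot go negative.

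**3. What a count from item 1 leaves open**

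Let n subjects complete the form and k tick a given box. The number who worsened on that attribute, W, is not observed. If ticks are taken at face value, then 0 ≤ W ≤ n − k. Section 10.2 gives n as at most 10. The values of k below are assumptions, because the documents give none:
- k = 2: W lies between 0 and 10 − 2 = 8.
- k = 4: W lies between 0 and 10 − 4 = 6.
- k = 7: W lies between 0 and 10 − 7 = 3.

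With k = 4, the same form is compatible with nobody worse and with more subjects worse than better. The gateway can also lose information the other way: a subject who feels better hydrated but sees no change in appearance answers NO and does not reach the hydration box.

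**4. How the item is answered**

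The instruction concerns how the area looks. The hydration box refers to how skin feels, and pliability is also judged largely by touch. The instruction and these two boxes do not match well.

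**5. What a YES can be attributed to**

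The study has a single arm, and every subject has both the lower facelift and Renuvion, with Renuvion applied to the lower face and neck (Sections 4.1 and 7.2). No answer on the PSQ separates the two.

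**The case against.** The strongest reply is that Outcome 9 is the whole PSQ. Item 2 is balanced, item 3 allows NO, no success rule exists and the analysis is descriptive. A reader might infer from item 1 that Outcome 9 must come out as benefit; the documents do not support that. Nor can item 1 record only improvement, since NO registers its absence. Nor would worsening be recorded as zero: the form has no field for it, so it is unmeasured. All of this stands and limits the point to item 1.

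Worsening can also surface elsewhere. GAIS has three worse categories. Histology (Section 4.3.4.1) can move in either direction on elasticity and hydration markers. Adverse events are elicited at each follow-up visit (Section 8.3) and the definition in Section 8.1.1 is broad. This stands too, but none of these gives a subject's rating of hydration or elasticity to set beside the item 1 counts.

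That facelift and device cannot be separated is a consequence of the single-arm design and affects GAIS equally. This is correct, and rewording the form does not cure it. Asking the same questions about the mid/upper face might look like a control. It would not be one, because the lower facelift and the device both act on the lower face.

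Finally, nothing stops a subject from answering by feel while holding a mirror, and no figure in the documents supports a claim that nearly everyone will answer YES. Both are fair. The mirror-and-photo point is a matter of clearer instruction.

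**Conclusion.** The point holds for item 1. It offers no response for worsening on any of its five named attributes, and a NO or blank merges unchanged with worse. Because no other structured subject-reported item covers hydration, elasticity or skin quality, the subject's own report on the study-purpose attributes is one-directional and open to being read as Renuvion benefit.

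The size of any distortion cannot be estimated from the documents. All that can be said is that up to n − k of n subjects could have worsened unseen on an attribute that k subjects ticked. This assumes that ticks are taken at face value and that subjects do not use the free-text line under YES to report a decline.

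The consequence is modest. This is one item within the ninth of ten outcomes, in a descriptive post-market study of up to 10 treated subjects, and no decision rule depends on it. It is worth correcting because the remedy is cheap and the sponsor already uses balanced scales in item 2 and GAIS.

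**What to change.** Replace item 1 with one row for each of hydration, elasticity/pliability, skin quality, youthfulness and radiance, each answered improved, no change or worse. Remove the YES gateway so that every subject answers every row. Instruct subjects to judge hydration and pliability by feel as well as by mirror. Keep items 2 and 3 unchanged.

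In the analysis section, state that all three categories will be reported for each attribute with the number of respondents, and that PSQ results reflect lower facelift plus Renuvion combined. Do not add mid/upper-face rows as a control.

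The cost is one revised page and IRB approval. The figures may look less favorable. Subjects already past Day 180 will have completed the existing form and must be reported separately, which divides an already small group.

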### 2. How would you characterize your satisfaction with the treatment?

- ☐ Very Satisfied
- ☐ Satisfied
- ☐ Slightly Satisfied
- ☐ Neither Satisfied nor Dissatisfied
- ☐ Slightly Dissatisfied
- ☐ Dissatisfied
- ☐ Very Dissatisfied

### 3. Would you recommend this treatment to your friends and family members (*check one*)?

- ☐ YES ☐ NO

*Thank you for completing this questionnaire.*

Subject Initials: \_\_\_\_\_

Date: \_\_\_\_\_ (DD/MON/YYYY)

## APPENDIX B: PROTOCOL REVISIONS LOG

VERSION	DATE	SIGNIFICANT REVISIONS
1.0	11 May 2022	Initial release
2.0	13 Sept 2022	
 
Added ASA Physical Classifications added to inclusion/exclusion criteria.
 
Study recruitment duration updated to 6 months.
 
Added biopsy at D7 for immunochemistry (SOSC3 and iNOS).
 
Revised punch biopsy from 3mm to 3-5mm. Added punch biopsy risks.
 
GAIS for Investigator and Subject added to D45, D90, and D180
 
PSQ added to D180.
 
Clarified balancing procedure request process and treatment sides for Arm B.
 
Date and version updated.
 

3.0	03 Apr 2023	
 
Updated number of sites from 1 to 2
 
Addition of new indication language
 
Addition of Renuvion procedure video for proper biopsy placement
 

4.0	24 Apr 2023	
 
Addition of option for the site to use Apyx One generator
 
Removal of [name] from Internal Responsibilities section
 

5.0	24 Aug 2023	
 
Updated number of sites from 2 to 3.
 
Updated number of subjects from 12 to 10.
 
Changed inclusion criteria from full facelift to lower facelift.
 
Removed randomization arms. All subjects are now receiving the same treatment (Lower Facelift with Renuvion).
 
Updated biopsy location for all patients. They will be taken from the upper preauricular area where no treatment occurs and the lower preauricular area by the ear lobule.
 
Histology updated to compare untreated skin sections to treated sections for all patients.
 
Removal of iNOS and SOSC3 analysis.
 
Removal of Day 7 biopsy.
 
Changed Renuvion APR treatment settings from investigator's standard clinical practice to 4 passes at 80% power and 1.5LPM.
 
Added [name] as a Principal Investigator.
 
Changed Vice-President, Quality Assurance & Regulatory Affairs from [name] to [name].
 
Changed Clinical Affairs personnel from [name] to [name]
 

6.0	10.02.2023	
 
Updated Study Purpose & Brief Study Overview sections to add estimate biological skin age using DNA methylation
 
Added Outcome Measure "Change in estimated biological age from baseline to D180"
 

Protocol Number: APX-21-04

Effective Date: March 19, 2024

Revision No: 7.0

Title: Histological Evaluation of Human Skin Biopsies to Assess the Effects of Renuvion APR Treatment as an Adjunct Procedure in Facelift Surgery

		
 
Added University of Miami Miller School of Medicine Center for Genome Technology to Table 1.2-1
 
Added section 4.3.4.8 to describe DNA Methylation
 
Added Literature Reference 20
 

7.0	03.19.2024	
 
Remove [name] from table 1.2-1 since he is no longer participating on study
 
4.3.4.1 elaborate on when to collect biopsy samples
 
Updated table 5 to add subject PSQ
 
5.3 Add exclusion criteria to exclude Subjects who has had a prior facelift, neck lift or Renuvion treatment in the area to be treatment
 
Section 7.2 Clarify that a video or photograph can be used to capture the location of the biopsies.
 
Protocol Synopsis pg 5 & Study Purpose pg 20 correct typos
 
Section 7.4.4 updated for grammar errors
 

